9.1.3. Follow up of Adverse Events

The investigator will follow a non-serious AE until resolution, stabilization, or the End of Study Visit. The investigator will follow an SAE (regardless of relationship to study drug) until the event resolves, stabilizes, or becomes non-serious. All AEs identified on the last scheduled contact must be recorded on the AE page of the eCRF and the current status (ongoing or resolved) will be noted. In addition, SAEs will be reported to Product Safety according to the reporting guidelines identified in Section 9.2.2.

9.2. Monitoring of Adverse Events

9.2.1. All Adverse Events

All AEs will be analyzed for safety. Those meeting the definition of SAE must be reported using the SAE Form. Subjects should voluntarily report any AEs or report AEs in response to general, non-directed questioning (e.g., "How has your health been since the last visit?"). For each AE volunteered by the subject, the investigator should obtain all the information required to complete the AE page of the eCRF, in accordance with the guidelines that accompany it.

All AEs, regardless of seriousness, severity, or presumed relationship to study therapy, must be recorded using medical terminology in the source document and on the eCRF. Whenever possible, diagnoses should be given when signs and symptoms are due to a common etiology (e.g., cough, runny nose, sneezing, sore throat, and head congestion should be reported as "upper respiratory infection"). Investigators must record on the eCRF their opinion concerning the relationship of the AE to study therapy. All measures required for AE management must be recorded in the source document and reported according to sponsor instructions.

Any non-serious AE that occurs after the dose of study drug must be reported in detail on the appropriate eCRF page and followed until resolution, stabilization, or the End of Study Visit. The description of the AE will include description of event, date of onset, date of resolution, investigator assessment of severity and relationship to study drug, seriousness, any required treatment or evaluations, and outcome.

The sponsor assumes responsibility for appropriate reporting of AEs to the regulatory authorities. The sponsor will also report to the investigators all serious AEs that are unlisted and associated with the use of the drug. The investigators must report these events to the appropriate Institutional Review Board (REC) in accordance with local regulations.

9.2.2. Serious Adverse Events

All SAEs occurring during clinical trials must be reported within 24 hours to Product Safety.

The cause of death of a subject in a clinical trial, whether the event is expected or associated with the investigational agent, is an SAE.

The initial report of an SAE may be made by e-mail or facsimile (fax). The investigator must provide the minimal information: i.e., protocol number, subject's initials and date of birth, subject number or medication code number, nature of the AE and investigator's attribution.

All oral reports of an SAE must be confirmed within 24 hours by a written, more detailed report and signed by the investigator. For this purpose, the sponsor will provide the investigator with the Serious Adverse Event Form for Clinical Trials.

All SAEs that have not resolved by the end of the study, or that have not resolved upon discontinuation of the subject's participation in the study, must be followed until either:

- the event resolves,
- the event stabilizes, or
- the event becomes non-serious

The investigator should report any follow-up information as it becomes available.

9.2.3. Pregnancies

Pregnancies occurring after the first dose of investigational product and during participation of the study are considered immediately reportable events. While not considered a SAE unless a serious criterion is met, pregnancies occurring in subjects enrolled on the study must be reported and followed to outcome. The investigator should complete the pregnancy report eCRF within one working day of knowledge of the pregnancy. Following delivery or termination of pregnancy, the follow-up pregnancy report form should be completed on the pregnancy CRF. Spontaneous abortions should always be reported as SAEs. Follow-up information regarding the outcome of the pregnancy and any postnatal sequelae in the infant will be required.

9.3. Contacting Sponsor Regarding Safety

Any AE considered serious by the investigator, or that meets the SAE criteria stated in this protocol, must be reported to Product Safety within 24 hours from the time that study site personnel first learns of the event. The study site must enter the SAE into the EDC system.

Source documents will be requested from the study sites for SAEs and should be provided to Product Safety. If the subject is hospitalized during the study, a copy of the hospital discharge summary should be provided to the Product Safety as soon as it becomes available.

10. SUBJECT COMPLETION

10.1. Completion

Subjects who withdraw from further administration of study drug or who withdraw their consent to be followed or are lost-to-follow-up before completion of Visit 3 (Month 6) will not be considered to have completed the study.

10.2. Withdrawal

All subjects have the right to withdraw from study drug administration and/or study evaluations at any time, for any reason, without prejudice; nonetheless, investigators should attempt to encourage subjects to complete the protocol even if the subject has withdrawn from study drug so that continued observation and follow-up measurements may be obtained. The investigator may discontinue a subject's participation in the study at his/her discretion for reasons including, but not limited to, the following:

- 1. Subject experiences a serious or intolerable AE that, in the opinion of the investigator, requires withdrawal from the study.
- 2. Subject is in violation of the protocol.
- Subject develops a condition during the course of the study that makes it unwise to continue with the trial.
- 4. Subject requires a medication that is prohibited by the protocol.
- 5. Subject requests an early discontinuation for any reason.

At any point, the investigator may discontinue the subject's study participation at his/her discretion and ensure the subject receives appropriate medical care; the investigator may also consult the medical monitor to discuss out-of-range test results.

10.2.1. Handling of Withdrawals

Subjects will be free to withdraw from further study drug administration and further follow-up the study at any time. Subject participation in the study may be stopped at any time at the discretion of the investigator or at the request of the sponsor.

Whenever possible, all subjects who withdraw from further study drug administration should be encouraged to remain on-study for further follow-up through the subject last scheduled visit. However, should a request for early withdrawal from the study with no further follow-up be made, the subject should be encouraged to return to the study site for a last follow up visit and undergo all end of study/early termination assessments.

When a subject withdraws from further administration of study drug or the study prior to completing Visit 3 (Month 6), the reason for withdrawal is to be documented on the eCRFs and in the source document.

10.2.2. Replacements

Subjects who discontinue participation in the study for any reason after dosing will not be replaced.

11. STATISTICAL METHODS

The emphasis of the analysis will be with respect to description and estimation rather than hypothesis testing. The following statistical sections describe the general analytic methods to be implemented to assess the overall study objectives. More detailed descriptions of the methodology will be provided in the Statistical Analysis Plan (SAP).

11.1. Sample Size

It is expected that up to 300 subjects from Phase 2 (104-201403) or Phase 3 (104-201508) clinical trials will be enrolled into this study. The sample size was not based on any power calculation.

11.2. Analysis Sets

The following definitions will be used to derive the analysis sets for this study.

Safety Analysis Set: The safety analysis set will include all subjects who receive at least one dose of study drug.

11.3. Description of Subgroups to be Analyzed

Key safety data will be described for the following subgroups using the safety analysis set:

- Subject Demographics
 - Gender

Additional demographic and baseline characteristic subgroups will be considered and identified in detail in the SAP.

11.4. Subject Demographics, Baseline Disease Status, and Disposition

Descriptive statistics for subject demographics, baseline disease status, and subject disposition will be provided. If feasible, a Kaplan-Meier plot of time-to-study withdrawal will also be estimated. Protocol deviations will be analyzed by aggregate summary and/or line listings if the number of deviations is small.

11.5. Efficacy Evaluations

Not applicable

11.6. General Analytic Methods

The primary analytic approach for this trial will be descriptive. Summary statistics will be calculated and where relevant, 95% confidence intervals presented. Details of the analysis will be described in the SAP.

11.7. Safety Evaluations

Safety evaluations include:

- Vital Signs, Height and Weight Measurements
- Tympanometry
- Audiometry
- Otoscopy
- C-SSRS Assessment
- Concomitant Medications
- Adverse events

11.7.1. Adverse Events

Version 18.1 of Medical Dictionary for Regulatory Activities (MedDRA) will be used to code all AEs.

The primary analysis of AEs will consider only treatment emergent AEs (TEAEs), events occurring for the first time, or worsening during or after the first dose of study drug. Subject incidence of TEAEs and SAEs will be tabulated by preferred terms and system organ class. These analyses may also be tabulated by visit, time of onset and/or cumulative exposure. In addition, severity and relationship to study drug will also be presented. Adverse events will be presented by descending order of frequency in MedDRA system organ class and preferred term.

Subgroup analyses of AEs by gender will be examined. Listings of all SAEs, AEs leading to study withdrawal, and deaths on-study will also be included. Duration and outcome of each AE will be reported in subject listings.

11.7.2. Vital Signs

The analysis of vital signs will include descriptive statistics for the change from baseline to each post-baseline visit where vital signs are collected. The change from baseline to the worst post-baseline value (increase/decrease) may also be examined. Weight measurements for baseline and post-baseline visits will be tabulated as will height measurements for baseline.

11.7.3. Otoscopic Examinations

Observations recorded during the conduct of otoscopic exams will be descriptive. The number and percent of subjects presenting with each otoscopic classification will be provided by study visit using shift tables where appropriate. Data will be tabulated separately for the treated and untreated ear.

11.7.4. Audiometry Assessments

Descriptive summary statistics and/or shift tables for audiometric assessments of air and bone conduction thresholds at each frequency will be provided by study visit. In addition, the pure tone average (PTA) and bone conduction average (BCA) will be calculated as the average air or bone conduction threshold for frequencies of 500, 1000, and 2000.

Air-Bone Gap assessments at each frequency and study visit will be tabulated as the proportion of subjects with air minus bone conduction thresholds of:

- $\leq 10 \text{ dB or}$
- > 10 dB.

All audiometry assessments will be tabulated separately for the treated and untreated ear.

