8.2.3. Tympanometry

Tympanometry assessments will be used to assess the mobility and compliance of the tympanic membrane, pressure and volume in the middle ear, and function of the tympanic membrane, ossicles and eustachian tube. Tympanograms will be completed in both ears at all study visits. Subjects wearing hearing aids should be instructed not to wear their hearing aids during the tympanometry assessment.

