8.2.4. Audiograms

Audiometric assessments will be used to assess hearing function in both ears. Audiograms should be conducted at 500, 1000, 2000, 4000 and 8000 Hz for both air and bone conduction at all study visits. Both air and bone conduction thresholds will be assessed. Pure tone averaging bone and air conduction testing will be done at 500, 1000, and 2000 Hz frequencies. Subjects wearing hearing aids should be instructed not to wear their hearing aids during the audiogram.

Audiometric assessments must be conducted in accordance with American-Speech-Language-Hearing Association Guidelines (ASHA, 2005). Equipment calibration must be current and documented. The audiometric assessments must be conducted by a licensed audiologist or a

qualified assistant with appropriate training under the direct supervision of a licensed audiologist.

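### Section 11.7.4 reports the air-bone gap only as the proportion at or below, or above, 10 dB at each visit, so the size of an individual ear's worsening cannot be seen

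*Combined protocol and SAP*

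**What the plan says.** Section 8.2.4 requires the raw material at every visit: "Audiograms should be conducted at 500, 1000, 2000, 4000 and 8000 Hz for both air and bone conduction at all study visits". The gap in dB can therefore be derived for each subject, ear, frequency and visit.

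Section 11.7.4 plans three audiometric outputs:

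- Thresholds: "Descriptive summary statistics and/or shift tables for audiometric assessments of air and bone conduction thresholds at each frequency will be provided by study visit".
- Averages over 500, 1000 and 2000 Hz: "the pure tone average (PTA) and bone conduction average (BCA) will be calculated as the average air or bone conduction threshold".
- The gap: "Air-Bone Gap assessments at each frequency and study visit will be tabulated as the proportion of subjects with air minus bone conduction thresholds of" no more than 10 dB, or more than 10 dB. The upper category is open-ended.

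The section closes with "All audiometry assessments will be tabulated separately for the treated and untreated ear". For the gap it names no dB summary, change from baseline, shift table or further band.

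Section 11.6 states generally that "Summary statistics will be calculated and where relevant, 95% confidence intervals presented" and leaves detail to the SAP. The text available for this review contains no separate SAP section on audiometry.

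**The concern.** A conductive loss raises the air threshold and leaves the bone threshold alone, so the gap is the quantity that measures its size. An intratympanic injection passes through the tympanic membrane, which makes conductive loss an obvious local harm to describe. Section 1 also says that Meniere's disease fluctuates and ends in sensorineural loss in the affected ear. A rise in the air threshold alone is therefore ambiguous, and pairing it with the bone threshold of the same ear is what separates the two explanations.

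In a descriptive safety study the useful result is how many treated ears worsened and by how much, above all in the worst-affected ears. A visit-by-visit proportion on either side of one cut answers neither question. The plan is also uneven: Section 11.7.2 gives vital signs a change from baseline and Section 11.7.5 gives tympanograms a baseline shift table, but the gap is explicitly given neither.

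**Working it through.** The plan states no figure on this point, so there is nothing to reproduce. The check applies the stated cut to example ears and then asks what the other planned outputs would show.

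**Inputs.** From the documents: the 10 dB cut (Section 11.7.4) and up to 300 subjects (Section 11.1), hence up to 300 treated ears. Assumed, because the documents do not give them: thresholds in 5 dB steps, the share of ears above 10 dB at baseline (nominally 5%, 10% or 20%), and the number and size of the worsenings.

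**Step 1: single ears.** Gap = air threshold minus bone threshold.

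| Baseline (dB) | Follow-up (dB) | Change (dB) | Category at baseline and follow-up |
|---|---|---|---|
| 15 | 40 | +25 | above 10, above 10 |
| 20 | 45 | +25 | above 10, above 10 |
| 10 | 15 | +5 | at most 10, above 10 |
| 0 | 10 | +10 | at most 10, at most 10 |

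The two largest worsenings leave the table as it was, and the smallest one moves it.

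**Step 2: a group of 300 ears.** Suppose 10 ears already above 10 dB each worsen by 25 dB.

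- Proportion above 10 dB: unchanged. In the three simulated baselines it was 11/300 = 3.7%, 35/300 = 11.7% and 64/300 = 21.3%, both before and after.
- Mean gap: rises by 10 × 25 / 300 = 0.83 dB. With 5 such ears the rise is 5 × 25 / 300 = 0.42 dB. With 30 it is 30 × 25 / 300 = 2.5 dB, which needs at least 10% of ears above 10 dB at baseline.

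Now suppose instead that 10 ears go from 10 to 15 dB.

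- Proportion above 10 dB: rises by 10/300 = 3.3 percentage points, for example from 11/300 = 3.7% to 21/300 = 7.0%.
- Mean gap: rises by 10 × 5 / 300 = 0.17 dB.

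The table reacts to the smaller harm and not to the larger one.

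**Step 3: cancellation.** Only visit proportions are planned. If 3 ears improve from 15 to 0 dB and 3 worsen from 0 to 40 dB, the count above 10 dB changes by −3 + 3 = 0. Three new gaps of 40 dB do not appear.

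**Step 4: what the other outputs recover.** If air and bone means are both reported on the same ears, mean air minus mean bone equals the mean gap. The spread of the gap does not follow, because Var(gap) = Var(air) + Var(bone) − 2 Cov(air, bone) and no covariance is planned. Nor do its percentiles, its maximum or any ear's change. Threshold shift tables are optional under the and/or wording. Even if produced, they would show air and bone movements separately, without saying whether they occurred in the same ear. PTA and BCA have the same limit. Tympanometry gives a change of type, not a number of decibels.

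**The case against.** The strongest reply is that conductive loss is covered elsewhere. Air thresholds enter the summaries in dB, by frequency and ear. On tympanometry, Section 8.2.3 says "Tympanometry assessments will be used to assess the mobility and compliance of the tympanic membrane, pressure and volume in the middle ear", and Section 11.7.5 tabulates shifts from baseline. Otoscopy records the presence and size of perforations. Clinically important hearing worsening can qualify as an adverse event under Section 9.1, and Section 14.7 provides for periodic review of ear and labyrinth events. This stands as far as it goes: a reader might infer that the gap table is the plan's only view of conductive loss, and the documents do not support that. It does not answer the narrower point, since none of these outputs gives the size of an ear's change in gap. Adverse event capture is also conditional: abnormal test results count only under the conditions listed in Section 9.1, and perforations only if they enlarge and remain unresolved at study end.

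A reader might also infer that large worsening hides below the cut. It hardly can: from a zero gap, at most 10 dB is possible without crossing, and 15 to 20 dB needs a negative starting gap of −5 or −10 dB. Nor does the plan treat a crossing as a new conductive loss in a subject, because it reports proportions at visits and classifies no individual changes.

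A loss of statistical power is another tempting inference. Section 11 puts description and estimation ahead of testing, Section 11.1 gives no power basis, no test of the gap is planned, and the documents give no gap distribution. Any power figure, or any estimated share of missed worsenings, would rest on invented gaps and measurement noise.

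Finally, detail is deferred to the SAP. That is fair, and the point lapses if the SAP supplies it. But Section 11.7.4 already states a specific two-level rule, and nothing in the text reviewed adds to it.

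**Conclusion.** The point holds as a limitation of one planned output. The gap table cannot show worsening in ears already above 10 dB, responds to a single 5 dB step at the cut, and lets opposite crossings cancel. The remaining audiometric and middle-ear outputs do not give each ear's change in gap. The size can only be illustrated: with 300 ears, 10 worsenings of 25 dB above the cut move the proportion by nothing and the mean gap by 0.83 dB (0.42 dB for 5 ears, 2.5 dB for 30). These figures rest on assumed numbers of affected ears and assumed 5 dB steps. The documents do not say how many ears start above 10 dB, and if very few do, the part about ears above the cut matters less. The point should be addressed because safety is the only objective and the remedy needs no new data. It does not show that the plan would miss conductive harm altogether.

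**What to change.** In Section 11.7.4 or the SAP, keep the existing two-category table and add, by ear, frequency and visit:

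1. Descriptive statistics for the gap in dB and for its per-ear change from baseline, including an upper percentile and the maximum, with a 95% CI for the mean change.
2. A baseline-by-visit shift table for the gap with more than two bands. Cuts at 10, 20 and 30 dB would serve as an example. The documents prescribe no bands, so they should be fixed before the data are summarised.

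The cost is wording, programming and longer output: 5 frequencies × 2 ears × 3 visits = 30 sets of gap statistics, and 5 × 2 × 2 post-baseline visits = 20 sets of changes. No extra assessments or subjects are needed. Changes seen at a single visit should be read with measurement noise in mind, and the untreated ear gives a useful comparison. If a separate SAP already contains these summaries, no change is needed.

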11.7.5. Tympanometry

Shift tables representing the proportion of subjects with changes in their tympanogram from baseline to each post-baseline study visit will be calculated. Tympanogram changes will include both the type of tympanogram (A, B-small volume and/or normal, B-large volume, or C).

11.7.6. Concomitant Medications

Concomitant medications will be coded by WHO Drug and will be tabulated by drug class and preferred drug name.

11.7.7. C-SSRS

The C-SSRS will be administered at each visit using the appropriate version i.e. Baseline or Since Last Visit. Analysis of this scale will be performed on the Safety Analysis Set.

11.7.7.1. C-SSRS: Baseline Version

The C-SSRS assessment will be administered at all study visits. The Since Last Visit version of the C-SSRS will be used for subjects enrolling directly (within 1 month) from Study 104-201508 while the Baseline version will be used for all other subjects. The Since Last Visit version of the C-SSRS will be used at all subsequent visits. The Baseline version of the scale captures both suicide ideation and suicide behavior (lifetime). There are 5 suicidal ideation questions, each captured as yes/no for the subject's lifetime. Additionally, a sixth suicidal ideation variable will be created to indicate if there was any ideation, regardless of type. There are 4 suicidal behavior questions, each captured as yes/no for the subject's lifetime. A fifth suicidal behavior variable will be created to capture if there was any suicidal behavior regardless of type. An additional question asks if suicidal behavior is present during the visit. All suicidal ideation and behavioral variables as outlined here will be tabulated overall and by treatment group. All C-SSRS data will be included in data listings. There is no inclusion or exclusion criterion associated with the Baseline C-SSRS score.

11.7.7.2. C-SSRS: Since Last Visit Version

The Since Last Visit version of the C-SSRS will be administered at each study visit including Visit 1 or after Visit 1 depending on whether the subject was a participant from Study 104-

201403 or 104-201508. The same overall individual variables for suicidal ideation and behavior will be assessed as in the Baseline version. In addition, overall suicidality (yes/no) will be defined as any subject having any suicidal ideation or behavior since the last visit. All suicidal ideation and behavior variables will be tabulated overall and by treatment group for each study visit. All C-SSRS data will be included in data listings.

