- 3. Subject has a history of immunodeficiency disease.
- Subject has active or recent (<1 month prior to screening) middle ear disease, including but not limited to: chronic otitis media, acute otitis media, middle ear effusions, middle ear atelectasis, or cholesteatoma.
- 5. Subject has an abnormality of the tympanic membrane in the affected ear that would increase the risk associated with intratympanic injection including but not limited to a monomeric, atelectatic or atrophic tympanic membrane.
- 6. Subject has a history of tympanostomy tubes that includes evidence of perforation or lack of closure.
- 7. Subject has a history of previous endolymphatic sac surgery.
- 8. Subject has a history of previous use of intratympanic gentamicin in the affected ear.
- 9. Subject has history of drop attacks.
- 10. Subject has used systemic steroids within 1 month prior to Visit 1.
- 11. Subject has had intratympanic steroids within 1 month prior to Visit 1.
- 12. Subject has experienced an adverse reaction to intratympanic injection of steroids.
- 13. Subject has a hypersensitivity to dexamethasone or any of the excipients in OTO-104.
- 14. Subject has any other clinically significant illness or medical condition that, in the investigator's and the medical monitor's opinion, would prohibit the subject from participating in the study.
- 15. Subject has participated in a clinical trial within 30 days of Visit 1, not including the OTO-104 Phase 3 study (104-201508).

Criteria for Evaluation:

Safety Evaluations:

Key safety assessments include:

- Adverse events
- Audiometry assessments
- Tympanometry
- Local tolerability (otoscopic examinations)
- Vital sign measurements
- Columbia-Suicide Severity Rating Scale (C-SSRS): Baseline and Since Last Visit versions

Other Evaluations:

• Meniere's symptom questionnaire

Statistical Methods:

This is an open label safety study with one treatment group. All statistical analyses will be descriptive in nature.

Investigational Product, Dosage and Mode of Administration:

OTO-104 12 mg, single, intratympanic injection, 0.2 mL

Duration of Treatment:

Single IT injection given at Day 1 and Month 3

Reference Therapy, Dosage and Mode of Administration:

None

Time and Events Schedule: See Table 1.

Table 1: Time and Events Table

	Screening/ Baseline/Dose No. 1	Follow-up/ Dose No. 2	End-of-Study/ Early Term.	Unscheduled Visit
	Visit 1	Visit 2	Visit 3 ²	Unscheduled
Procedure	Day 1	Month 3 (± 2 weeks)	Month 6 (± 2 weeks)	N/A

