5. RANDOMIZATION AND BLINDING

This study is an open-label study with all subjects receiving OTO-104; therefore, no randomization or blinding is required.

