8.2.6. C-SSRS Assessment

The C-SSRS assessment will be administered at all study visits. The Since Last Visit version of the C-SSRS will be used for subjects enrolling from Study 104-201508 while the Baseline version will be used for all subjects enrolling from Study 104-201403. The Since Last Visit version of the C-SSRS will be used at all subsequent visits. Any subject with a positive score on the Baseline version or an appearance of any new suicidal ideation or suicide behavior since the Baseline version (whether administered in this study or Study 104-201508) should be referred to their primary care provider for follow-up.

If a subject has any post-Baseline C-SSRS score of 1-3 for Ideation (i.e., a "yes" answer to Questions 1, 2, or 3) or a "yes" response to the Non-Suicidal Self-Injurious Behavior question) and the score is higher than the Baseline C-SSRS score, then this assessment should be recorded as an adverse event (AE). This information is reported as indicated in Section 9.1. (Possible AE terms: Suicidal plans, Suicidal ideation, Suicidal tendency, Suicidal behavior, Suicidal intention, Suicidal depression, Active suicidal ideation, Passive suicidal ideation, Self-injurious behavior without suicidal intent).

If a subject has any post-Baseline C-SSRS score of 4 or 5 for Ideation (i.e., a "yes" answer to question 4 or 5) and/or any questions answered yes for Suicidal Behavior (with the exception of a "yes" response to the Non-Suicidal Self-Injurious Behavior question), and this was not observed at Baseline, then this assessment should be recorded as a serious adverse event (SAE). This information is reported as indicated in Section 9.2.2.

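### The planned C-SSRS tables are split by a treatment group the study does not have and do not set post-dose answers against the subject's own pre-dose answer, so on their own they do not separate new from pre-existing suicidality

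*Combined protocol and SAP*

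**What the plan says.** The design has one arm. The Synopsis (Statistical Methods) states "This is an open label safety study with one treatment group", and Section 5 states "This study is an open-label study with all subjects receiving OTO-104; therefore, no randomization or blinding is required". Section 11.1 plans for at most 300 participants, drawn from studies 104-201403 and 104-201508.

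The C-SSRS tables are nevertheless laid out by arm. For the Baseline version, Section 11.7.7.1 says "All suicidal ideation and behavioral variables as outlined here will be tabulated overall and by treatment group". For the Since Last Visit version, Section 11.7.7.2 says "All suicidal ideation and behavior variables will be tabulated overall and by treatment group for each study visit". The summary variable there has no link to the pre-dose state: "overall suicidality (yes/no) will be defined as any subject having any suicidal ideation or behavior since the last visit". Both sections also put all C-SSRS data into listings.

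Several other assessments are referred to baseline: vital signs by change (11.7.2), tympanometry by shift tables (11.7.5), otoscopy by shift tables where appropriate (11.7.3), and the symptom questionnaire by change and/or shift tables (11.8.1).

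Outside the analysis section, 8.2.6 does compare each subject with Baseline. For ideation scored 1 to 3, or non-suicidal self-injury, the rule reads "and the score is higher than the Baseline C-SSRS score, then this assessment should be recorded as an adverse event (AE"). Ideation scored 4 or 5, or suicidal behavior, becomes an SAE if it was not seen at Baseline. Section 11.7.1 tabulates TEAEs and SAEs by preferred term and system organ class.

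**The concern.** Safety is the only objective and there is no control arm, so a subject's own pre-dose state is the only internal comparator for a percentage at Month 3 or Month 6. The C-SSRS sections use the one table dimension that carries no information here, the arm, and leave out the one that does, the pre-dose answer. Section 8.2.6 treats the meaningful event as a rise over Baseline, but the analysis of the scale does not carry that idea through.

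At stake is how the C-SSRS tables can be read. A steady by-visit percentage could be the same subjects throughout, or new cases replacing resolved ones. A falling percentage could still hide new cases.

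**Working it through.** The plan gives no figure to reproduce. Section 11.1 says "The sample size was not based on any power calculation", and no C-SSRS rate appears anywhere. The check sets the sections side by side and adds one illustration.

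**1. The split.** With one group, the treatment-group column equals the overall column. No other grouping is defined for these tables.

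**2. What separate visit totals can show.** Let N subjects be assessed both before and after dosing, with a positive before and b positive after. The number newly positive lies between max(0, b − a) and min(b, N − a). N = 300 is the maximum in Section 11.1; a and b are assumed.

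| a (before) | b (after) | Fewest new | Most new | % of 300 | % of the N − a negative before |
|---|---|---|---|---|---|
| 0 | 6 | 6 | 6 | 2.0 | 6/300 = 2.0 |
| 15 | 15 | 0 | 15 | 0 to 5.0 | 0 to 15/285 = 5.3 |
| 15 | 21 | 21 − 15 = 6 | 21 | 2.0 to 7.0 | 6/285 = 2.1 to 21/285 = 7.4 |
| 30 | 15 | 0 | 15 | 0 to 5.0 | 0 to 15/270 = 5.6 |
| 30 | 30 | 0 | 30 | 0 to 10.0 | 0 to 30/270 = 11.1 |

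Only when nobody is positive before dosing do the totals fix the answer. A cross-tabulation gives the exact count in every row.

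The rows are also not like for like. Subjects from 104-201403 answer the lifetime form at Visit 1 and the Since Last Visit form afterwards. Read literally, the 11.7.7.2 table therefore omits them at Visit 1 and includes them later.

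**3. What the AE/SAE route adds.** Three hypothetical subjects under the 8.2.6 rules:

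| Subject | Before dosing | After dosing | Result |
|---|---|---|---|
| A, either feeder study | Nothing at Baseline | Ideation 2 | 2 exceeds none: AE (ideation 4–5 or behavior would be an SAE) |
| B, from 104-201403 | Lifetime form: ideation 3, long past | Ideation 2 | 2 does not exceed 3: not an AE under this rule |
| C, from 104-201508 | Parent-study Baseline form: ideation 3; parent-study final visit: none | Ideation 2 | AE if Baseline is the final visit; not an AE under this rule if Baseline is the Baseline form |

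Subject A is captured. Subject B can be missed because the Baseline version asks about the lifetime (11.7.7.1). Subject C depends on which Baseline is meant.

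**4. Which Baseline.** Two inconsistencies bear on this.

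- Section 8.1.1 takes the final-visit C-SSRS of 104-201508 as the baseline for subjects enrolling within 1 month. Section 8.2.6, in its referral sentence, counts new suicidality from the Baseline version given in either study. Its AE and SAE rules then say only Baseline.
- The C-SSRS note to Table 1 and Section 8.2.6 give the Since Last Visit form at Visit 1 to all 104-201508 subjects. Section 11.7.7.1 limits it to those enrolling within 1 month and gives everyone else the Baseline form. Subjects from 104-201508 who enroll later fall under both statements.

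**The case against.** The strongest reply is that the plan does report new cases, only elsewhere. A subject with no ideation or behavior at Baseline who later reports either meets one of the two 8.2.6 rules and so enters the TEAE or SAE tables. Six such subjects among 300 would show there as 6/300 = 2.0%, and the listings allow a subject-level comparison. This stands. A reader might infer that suicidality arising after injection cannot be told from earlier suicidality anywhere in the plan; the documents do not support that.

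A reader might also infer that treatment group is the only breakdown given for the scale. It is not. Results are by visit and by item, and Section 11.3 describes key safety data by gender, with the Synopsis listing the C-SSRS among key safety assessments. Nor is by-visit tabulation peculiar to this scale: Section 11.7.4 tabulates the air-bone gap by visit with no stated link to baseline.

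The AE route is still not a full substitute. It has the lifetime blind spot and the unsettled Baseline shown above. The general AE definition in 9.1 might bring in some recurrences, but that is left to judgment. Section 8.2.6 offers nine possible AE terms, so cases can scatter over preferred terms with no single count of new or worsened suicidality. Listings are not a summary.

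A simple shift table has limits too. Grouping ideation 1 to 3 would hide a rise from 1 to 3 that 8.2.6 records as an AE. A lifetime Visit 1 form cannot show onset since dosing. The fix has to allow for both.

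Finally, Sections 11 and 11.6 defer detail to the SAP. No separate SAP text was available to check, so a shift table may be specified there. The layout written in 11.7.7 would still need correcting.

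**Conclusion.** The point holds for the C-SSRS summary tables. Their treatment-group split is empty in a one-arm study, and by-visit counts without a cross-tabulation do not, on their own, separate new or worsened suicidality from pre-existing suicidality. The AE/SAE rules and tables cover subjects who were clear at Baseline. They can miss recurrence that stays within a lifetime Baseline score, and they rest on a Baseline that the sections define inconsistently.

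The treatment-group wording alone is clerical. The missing baseline comparison is worth acting on because safety is the only objective and the remedy is cheap. No size can be taken from the documents. The ranges above, such as 0 to 15 new cases of 300, rest on assumed counts and on all 300 subjects being assessed at both times. They show what the totals leave open, not what to expect.

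**What to change.** - In 11.7.7.1 and 11.7.7.2, delete the tabulation by treatment group.
- State which assessment is the C-SSRS baseline for each feeder study. Reconcile 8.1.1 with 8.2.6, and the Table 1 note and 8.2.6 with 11.7.7.1.
- In 11.7.7.2, add a shift table from baseline to worst post-dose category. Keep the ideation levels separate (none, 1, 2, 3, 4, 5, behavior) so that a rise within 1 to 3 is visible, and give the number and percent new or worse.
- Show it separately for 104-201403 and 104-201508, and label it by the form used. For subjects with the lifetime Baseline form, the result is new or worse than lifetime history. For subjects with the Since Last Visit form at Visit 1, it is new relative to the pre-dose period.

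The cost is wording in two analysis sections, a baseline definition, the reconciliation, and one table. No new assessments are needed. If the baseline is a parent-study assessment, those records must be linked. Cells will be sparse, so counts should stand beside percentages.
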